#### **2.7.5.1 Verbal declaration before surgery**

The research team will present the consultee with the same information as patients with capacity receive, and will offer the opportunity to discuss the study and ask questions. If the consultee gives verbal declaration for the patient to be involved in the trial, the patient will proceed to treatment allocation. The research team will record the name of the consultee and verbal declaration on the screening log and study summary sheet. If the consultee refuses to give verbal declaration on behalf of the patient, this will also be noted on the screening log. There is also a full consultee study information sheet available should the consultee want to read this before giving verbal declaration. The participant will remain free to withdraw agreement at any time up to the time of surgery without giving reasons and without prejudice to any further treatment. Additionally, as with patients who have capacity, if the personal or nominated consultee wishes to provide full written consent at this point they are free to do so. If the patient regains capacity their consent to continue will be sought.

#### **2.7.5.2 Verbal declaration over the phone**

In the case of patients who do not have capacity, where a personal consultee is unavailable in person, but contactable over the phone, if they are willing to provide a verbal declaration over the telephone after having the summary information sheet read to them, they can do so, and this will be documented on the verbal declaration form.

### **2.7.5.3 Written declaration after surgery**

The majority of these patients will regain consciousness and be comfortable the day after surgery. On the day after surgery, or the first available opportunity the research team will reassess the patient's mental capacity. If they are assessed to lack capacity, the research team will make all reasonable effort to contact the patient's family or known carer to act as a personal consultee. If a personal consultee cannot be reached via telephone call, then the research team will seek a nominated consultee. Where possible, the research team will seek to approach the same nominated consultee that previously agreed to the patient's participation upon review of the summary information sheet.

The consultee (either personal or nominated) will be given a consultee study information sheet and time for discussion with the research team. If the consultee agrees for the patient to continue in the study, they will be asked to sign a written declaration. The written declaration will state that in their view the person who lacks capacity would have wanted to continue to take part in the trial. If the consultee chooses to withdraw their participation at this point, the research staff will ask for consent to keep anonymised data already collected as part of the study.

### **2.7.6 Participants who regain mental capacity**

Mental capacity will be reassessed at the follow up visit where informed written consent is sought. If the patient is deemed by the research team to have regained capacity, written informed consent will be sought in the same fashion as described for those who had capacity to give verbal consent before surgery.

### **2.7.7 Participants who lose mental capacity**

If a participant loses mental capacity during their participation, before they are approached for informed written consent, the research team will seek a consultee. The consultee (either personal or nominated) will be given a consultee study information sheet and time for discussion with the research team. If the consultee agrees for the patient to continue in the study, they will be asked to sign a written declaration. The written declaration will state that in their view the person who lacks capacity would have wanted to continue to take part in the trial. If the consultee chooses to withdraw their participation at this point, the research staff will ask for consent to keep anonymised data already collected as part of the study.

### **2.7.8 Responsibilities**

The Principal Investigator (PI) is responsible for ensuring that the consent processes described above are followed at the hospital site.

The consultation and consent process will be undertaken by a registered medical practitioner or other healthcare professional who is a member of the research team with the approval of the site PI.

## **2.9 Trial treatments / intervention**

### **2.9.1 Trial treatment(s) / intervention**

The trial intervention is the use of continuous non-invasive blood pressure monitoring, visible to the anaesthetist from before induction of anaesthesia, until the patient has left the theatre and

moved to the post-anaesthetic care unit (“recovery”; PACU). All other aspects of the trial will be the same as the control/comparison group.

### **2.9.2 Trial control/comparison group**

The trial control/comparison group will have continuous non-invasive blood pressure monitoring applied by the research team. The readings will not be available, or visible to the clinical team treating the patient. Additionally, the alarms will be disabled, to ensure no information is obtained through visual or audible cues.

### **2.9.3 Measures common to the intervention and control groups**

The vast majority of the perioperative care provided to the control and intervention groups will be similar. Pre-operative care will be unaltered. Once group allocation has occurred, there will be no restrictions on choice of anaesthetic technique (for example, choice of general or regional anaesthesia, choice of drugs).

Management of the patient’s blood pressure will be at the sole discretion of the anaesthetic team treating the patient. Baseline blood pressure (systolic, mean, and diastolic) will be calculated as the average of 2 readings 5 minutes apart before administration of any anaesthetic drugs. Both control and intervention groups will have ‘standard non-invasive blood pressure monitoring’ regardless of the availability of CNAP to the treating anaesthetist, as shown in the trial diagram. The frequency of readings will be chosen by the treating anaesthetist

Continuous non-invasive blood pressure monitoring will continue until the patient moves to the PACU.

### **2.9.4 Compliance/contamination**

Compliance with treatment will be indicated by a number of measures

We anticipate that there will be times during the trial where the CNAP monitor is not recording. This can be for a number of reasons

- Calibration; every 30 minutes the CNAP cuff finger is switched. Recalibration takes place at this point. During this, a new blood pressure reading is unavailable for between 1m45s and 2m15s. At this point a non-invasive blood pressure reading from the native monitoring will be used to calibrate the CNAP monitoring. Blood pressure will be assumed to be unchanged during this period. As part of the feasibility study, the total recording time lost to calibration will be noted, and the method for managing this developed if required in the full study.
- Disconnection; The reasons for disconnection will be noted. If disconnection leads to >5 minutes without CNAP blood pressure monitoring, the patient will be excluded from the study analysis.
- Equipment malfunction; if the CNAP device malfunctions such that blood pressure monitoring is unavailable for >5 minutes the patient will be excluded from the study. The patient will receive routine care thereafter.

- Patient deterioration; If the patient deteriorates such that the treating clinician judges invasive blood pressure measurement is required, the patient will be excluded from the study.
- For other reasons not anticipated, anything that leads to >5 minutes of CNAP monitoring being unavailable will lead to patient exclusion. Details will be noted.
- For other reasons not anticipated, anything that leads to <5 minutes of CNAP monitoring being unavailable will not lead to patient exclusion, but an event marker will be included with details of the reason, and these will be collated to inform the refinement of the full study protocol, and will be an important part of the feasibility study.

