**Connection to CNAP monitor (the intervention)**

[figure not shown]
All patients included in the trial will have CNAP monitoring. The first cohort of patients (before) will have CNAP monitoring but the monitoring readings will not be visible to the

treating anaesthetist. The second cohort ('after') will have CNAP monitoring connected and visible for clinical use by the treating anaesthetist. In each case, normal clinical monitoring will be applied (non-invasive intermittent blood pressure monitoring). The systems will be applied on opposite arms, allowing the CNAP monitor to use its own automatic calibration without disturbing the standard monitoring.

The 'Standard monitoring' NIBP cuff will inflate approximately every 3-5 minutes, whereas the CNAP calibration cuff will only inflate every 20-30. As such we will recommend that the CNAP cuff is placed on the same arm as IV access is established, to offer the lowest chance of impeding flow of IV medication. However, this will not be mandatory, and ultimately it is up to the treating anaesthetist to determine the best position for IV access. Where there is an interruption in CNAP use because of IV access, the patient will be excluded from the study. This will form part of the feasibility analysis.

Figure 1 – Arrangement of Standard and CNAP monitoring, including suggested positioning of intravenous access.

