### 2.2.2 Secondary objective

Secondary objectives of the trial are to

- Assess the effectiveness of patient identification and screening
- Assess the effectiveness of the blinding
- Identify reasons for failure to recruit patients and screen fails

▪ Explore barriers and facilitators to recruitment

▪ Evaluate the robustness and completeness of data collection.

- Identify the proportion of patients with complete follow up at 30 days
- Identify the incidence of haemodynamic instability by evaluating the nadir blood pressure, the absolute time spent below blood pressure thresholds, and the proportion of anaesthetic time spent with a blood pressure outside defined limits.
- Identify the frequency of occurrence of technical difficulties with the CNAP equipment.
- Identify the incidence of post operative acute kidney injury, myocardial injury, stroke, and death in the post-operative period.

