### **2.3.3 Post-Operative Outcomes**

- Outcomes as per standardised definitions from the European Perioperative Clinical Outcome standards [28].
- Incidence of acute kidney injury in the 7 days post-operatively
- Incidence of myocardial injury in the first 3 days after surgery (Troponin>0.03ng/ml judged to be due to myocardial injury)
- Stroke: Thrombotic, embolic or haemorrhagic where there is a persistent residual motor, sensory or cognitive dysfunction
- Surgical site infection (superficial or deep, as per CDC definitions – see [29])
- Mortality: in hospital, and at 30 days post-operatively

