### 3.2 Laboratory assessments

There will be no laboratory assessments carried out specifically *by* the study. However, the study will record laboratory results of the serum creatinine concentration, serum troponin concentration, serum C-reactive Protein concentration, blood white cell count. These will be recorded from information available to the treating clinician only, and will not involve any research-specific samples.

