### **5.1 Data collection and management**

The Case Report Forms (CRFs) will be developed to collect all required trial data. On completion, original CRFs will be sent to Heartlands Hospital MIDRU, and a copy retained at the study site within research site files. The maintenance and upkeep of research files will fall to site specific research team and site PI. These files will be routinely checked upon monitoring visits conducted by MIDRU staff as per monitoring plan.

Data up to hospital discharge, and information on survival at 30 days will be recorded by the site research staff, based on the visit schedule detailed in table one and all data will be collected within CRF and stored in the research site file. Any information that is relevant to the participant's clinical care will be recorded in both researcher site file and patient care records, as to allow for transparency between clinicians and researchers of the participants health.

Data will be entered on to the trial database by staff based at the study site. The data entry clerk will enter data on to the trial database as soon as possible after receipt as per data management plan. The CRF will be reviewed for missing data, conflicting data, and other apparent errors. Where necessary, a data query will be raised for resolution by the study site.

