## **6. STATISTICAL ANALYSIS**

### **6.1 Determination of sample sizes**

This is a feasibility study, and as such the primary outcome is whether it is feasible to run the trial. However, secondary outcomes include;

- Nadir blood pressure; the lowest blood pressure recorded.
- Cumulative time spent with MAP <55mmHg, <65mmHg, 80mmHg.
- Post-operative incidence of acute kidney injury, myocardial infarction, stroke, infective complications and death.

The data produced during this feasibility study, and information currently available in the literature will be used to determine sample sizes for a full large-scale randomised controlled trial.

The main feasibility outcome is ability to successfully carry out the intervention, including screening, identification, consent, randomisation, and use of the equipment intra-operatively. It is anticipated that recruiting 30 cases will be sufficient to demonstrate feasibility, and allow improvements to the protocol to be made and tested.

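### Excluding patients who deteriorate after allocation removes likely higher-risk patients from outcomes that need no CNAP trace; the expected bias is small and the remedy is a few sentences

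*Combined protocol and SAP*

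**What the plan says.** Section 2.9.4 (Compliance/contamination) lists events after allocation that remove a patient. The rule for a worsening patient reads: "If the patient deteriorates such that the treating clinician judges invasive blood pressure measurement is required, the patient will be excluded from the study". The rule for a disconnected monitor reads: "If disconnection leads to >5 minutes without CNAP blood pressure monitoring, the patient will be excluded from the study analysis". Device malfunction, or any unforeseen cause, that makes CNAP unavailable for more than 5 minutes also leads to exclusion; losses under 5 minutes do not. Section 2.1.1 (Connection to CNAP monitor) adds: "Where there is an interruption in CNAP use because of IV access, the patient will be excluded from the study". It gives no duration, and says this will feed the feasibility analysis.

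Follow-up is described only in general terms. Section 5.1: "Data up to hospital discharge, and information on survival at 30 days will be recorded by the site research staff". The passage neither includes nor exempts excluded patients. Laboratory values come from routine care (section 3.2): "These will be recorded from information available to the treating clinician only, and will not involve any research-specific samples". Section 2.10.1 describes post-operative follow-up as a review of notes and blood results from after theatre.

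The outcomes affected include the secondary objective in section 2.2.2, "Identify the incidence of post operative acute kidney injury, myocardial injury, stroke, and death in the post-operative period", and the outcomes in section 2.3.3, such as "Incidence of acute kidney injury in the 7 days post-operatively". Section 6.1 gives them a further use: "The data produced during this feasibility study, and information currently available in the literature will be used to determine sample sizes". Section 6 defines no analysis set.

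**The concern.** Needing conversion to invasive pressure measurement is a marker of haemodynamic instability. The protocol's own premise (sections 1.1, 1.2 and 1.4) is that intraoperative hypotension goes with higher risk of kidney injury, myocardial injury, stroke and death. A rule that drops patients because they deteriorated therefore tends to drop those more likely to have the events being counted, and the most unstable haemodynamic records with them. CNAP is visible in only one cohort, so conversions could also differ between cohorts, in a direction the documents do not allow one to predict.

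Most of the affected outcomes do not need the lost recording. Total fluid and total vasopressor (section 2.3.2), the post-operative outcomes and mortality (section 2.3.3) and length of stay (section 2.3.4) can all be obtained without a CNAP trace. Excluding the patient from these gains nothing.

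At stake are the descriptive incidences and the before/after description that, together with the literature, inform the definitive trial.

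**Working it through.** **Is the patient kept anywhere?** Reading the relevant sections together:

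- Sections 2.9.4 and 2.1.1 state the exclusions. For malfunction, section 2.9.4 adds only that the patient then receives routine care.
- Table 1 and sections 3.3 and 5.1 set follow-up (days 1 to 7, discharge, 30 days) without mentioning excluded patients.
- Section 4.1.2 asks for serious adverse events from allocation to 30 days, again in general terms. Section 4.1.1 exempts events measured as outcomes from being reported as adverse events, and mortality is one of those outcomes. Safety reporting therefore does not clearly fill the gap, although section 4.3 has deaths reported separately.
- Sections 2.7.4.2, 2.7.5.3 and 2.7.7 address data already collected when a patient or consultee withdraws. There is no matching sentence for exclusion.
- Section 6 keeps no excluded patient in any analysis.

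**Size.** The plan states no exclusion rate, no AKI rate in hip fracture and no precision target, so it has no figure of its own to reproduce beyond 15 + 15 = 30. The calculation below rests on assumptions.

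Inputs:

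- N = 30, 15 per cohort (Trial Summary).
- AKI risk p: 5% in non-cardiac surgery and 10.9 to 16.4% in major abdominal surgery, both cited in section 1.2. In 30 patients this is 30 × 0.05 = 1.5 to 30 × 0.164 = 4.9 expected events.
- Excluded for deterioration: 1 or 2 of 30 (assumed), so e = 1/30 or 2/30.
- Risk in the excluded relative to the retained: RR = 2 or 3 (assumed).

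If r is the risk among retained patients, p = (1 − e)·r + e·RR·r, so r = p / [(1 − e) + e·RR].

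| p | e | RR | Divisor | r | Shift (points) |
|---|---|---|---|---|---|
| 5% | 1/30 | 2 | 1.0333 | 4.84% | −0.2 |
| 5% | 2/30 | 3 | 1.1333 | 4.41% | −0.6 |
| 10.9% | 1/30 | 2 | 1.0333 | 10.55% | −0.4 |
| 10.9% | 2/30 | 3 | 1.1333 | 9.62% | −1.3 |
| 16.4% | 1/30 | 2 | 1.0333 | 15.87% | −0.5 |
| 16.4% | 2/30 | 3 | 1.1333 | 14.47% | −1.9 |

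The expected shift is about −0.2 to −1.9 points. If the excluded carry the same risk as the rest (RR = 1), it is zero.

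**Bounds on a single realised data set**, with exact (Clopper-Pearson) 95% intervals and an assumed 3 AKI cases in 30:

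- All kept: 3/30 = 10.0% (2.1 to 26.5).
- Two excluded, both with AKI: 1/28 = 3.6%, a shift of −6.4 points.
- Two excluded, one with AKI: 2/28 = 7.1%.
- Two excluded, neither with AKI: 3/28 = 10.7%, a shift of +0.7 points.

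Within one cohort, an assumed 2/15 = 13.3% (1.7 to 40.5) becomes 1/14 = 7.1% or 2/14 = 14.3% after one exclusion. Every shifted value lies well inside the interval around its starting value.

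The documents give no basis for a similar calculation on nadir pressure or time below threshold, so none is offered.

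**The case against.** The case for leaving the text alone has several sound parts.

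*Rarity.* Exclusion criterion 4 (section 2.4.2) already removes patients judged beforehand to need invasive monitoring, so conversions should be uncommon. The other exclusions are mainly technical. This stands.

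*Importance.* The success parameters in section 2.2.3 are recruitment, screening, clinician willingness, equipment, data completeness and 30-day follow-up; event incidence is not among them. The main feasibility proportions use eligible or recruited patients as denominator (Trial Summary, sections 2.1 and 2.3.1), and reasons for not completing the protocol are reported. With 15 per cohort, chance error dominates. This stands and is why the point is minor.

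*Missing sources.* The trial flow diagram is not reproduced in the text available, and the data management plan is a separate document. Either might say what happens to excluded patients. This stands as a limit on certainty.

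*General follow-up text.* A reader might infer that follow-up stops at exclusion and outcome data are lost. The documents do not establish that. Sections 4.1.2 and 5.1 can be read as covering every allocated patient, and exclusion from analysis, the wording for disconnection, is compatible with continued data collection. But exclusion from the study, the wording for deterioration, points the other way. The fair description is unclear.

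*Generic omission.* Section 6 defines no analysis set for anyone, so its absence is not specific to these patients. True, but that leaves the exclusion rule as the only instruction on how to treat them.

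**Conclusion.** The point holds as a minor one. The deterioration rule is an explicit instruction that selects on a marker of outcome, and no section available keeps these patients for outcomes that need no CNAP trace. The technical exclusions mainly reduce numbers.

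The expected bias in AKI incidence is about −0.2 to −1.9 points. It rests on assumed numbers of exclusions, an assumed two- to three-fold risk, and AKI rates from other surgical populations.

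Three stronger readings should be resisted. The −6.4 point figure is a worst case that needs both excluded patients to have had AKI, so it is not an expected effect. The documents do not show a bias of known direction between cohorts. Nor do they show material harm to the feasibility conclusions or to the definitive trial's sample size, which will also draw on the literature. Confidence is high on what the exclusion rule says, and lower on whether follow-up would in practice stop.

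**What to change.** In sections 2.1.1 and 2.9.4, replace exclusion from the study or study analysis with:

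> The patient stays in the allocated cohort. Subject to consent, all outcomes that do not need a CNAP trace (total fluid, total vasopressor, post-operative outcomes, length of stay, in-hospital and 30-day mortality) are collected and analysed for all allocated patients. Loss of CNAP recording affects only CNAP-derived endpoints, and the patient counts as not having full CNAP data in the second outcome of section 2.3.1.

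In section 6, add:

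> For patients converted to invasive monitoring, the CNAP trace up to conversion is reported and flagged as truncated. Conversions and recording losses are reported by cohort and reason.

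Reconcile the IV-access wording in section 2.1.1, which has no duration, with the 5-minute wording in section 2.9.4.

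The cost is a few sentences. No new tests or visits are needed, because follow-up uses notes and routine blood results. The downside is that some haemodynamic records will be partial and may understate severity, hence the flag. Clinical management is unchanged.

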## **2.10 Blinding**

### **2.10.1 Methods for ensuring blinding**

The treating anaesthetist, and clinical team in theatre will not be blinded to the patient's treatment allocation, as they need to use the equipment in question.

The team performing follow up, which will involve reviewing the patient's notes and viewing their electronic blood test results and information will be blinded to the treatment the patient received, except where this is not possible due to organisational constraints. This part of the follow up will not require any viewing of the anaesthetic chart, and will be a review of entries in the notes *after* theatre. As such it should not be difficult for them to remain blinded.

The team performing statistical analysis will be blinded to the treatment allocation during the analysis phase.

The effectiveness of blinding will be reviewed as part of the feasibility outcomes, and if required altered for any further large-scale study based on this feasibility trial.

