**TRIAL SUMMARY**

Trial Title	Can continuous non-invasive monitoring improve stability of intraoperative blood pressure – A feasibility study in hip fracture surgery
ref. number	2019003AN
Clinical Phase	Phase III feasibility

Trial Design	Feasibility before-and-after trial	
Trial Participants	Adults undergoing surgery for repair of hip fracture	
Planned sample size	30 (15 control and 15 intervention patients)	
Treatment Duration	Intra-operative only.	
Follow-up Duration	In-hospital follow up to discharge, and mortality follow up to 30 days	
Planned Trial Period	From 01/06/2019-01/08/2019	
	Objectives	Outcome Measures
Primary	Demonstrate feasibility	Proportion of patients recruited who received the intervention, and completed follow up.
Secondary	Evaluate the incidence of intra-operative haemodynamic instability and post-operative adverse outcomes	Proportion of anaesthetic time with mean arterial pressure below set thresholds. Lowest recorded blood pressure. Amount of vasopressor and fluid given intraoperatively Post-operative incidence of acute kidney injury, myocardial infarction, stroke and death.

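### Sequential cohorts undercut the stated reason for follow-up blinding, its planned review has no measure, and the cardiac outcome carries two names

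*Combined protocol and SAP*

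**What the plan says.** **Blinding.** Section 2.10.1 leaves the theatre team unblinded and aims to blind those who collect follow-up data. Its reason is that they review only entries made after theatre: "This part of the follow up will not require any viewing of the anaesthetic chart". From this it infers: "As such it should not be difficult for them to remain blinded". It allows an exception, "except where this is not possible due to organisational constraints", and plans a check: "The effectiveness of blinding will be reviewed as part of the feasibility outcomes". Section 2.2.2 lists that check as a secondary objective. For analysts, 2.10.1 says: "The team performing statistical analysis will be blinded to the treatment allocation during the analysis phase".

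**Allocation.** Section 2.1.1 describes consecutive cohorts. "The first cohort of patients (before) will have CNAP monitoring", with the readings hidden from the anaesthetist. The second cohort "will have CNAP monitoring connected and visible for clinical use by the treating anaesthetist". The Trial Summary gives the size as "30 (15 control and 15 intervention patients".

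**Cardiac outcome.** The Trial Summary and 6.1 list myocardial infarction. Sections 2.2.2 and 2.3.3 list myocardial injury. Section 2.3.3 writes out a criterion for injury only (a troponin threshold, within three days of surgery, with a judgement about cause), and also refers to an external set of standardised perioperative definitions.

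**The concern.** Keeping assessors away from the anaesthetic chart protects blinding when both groups are recruited side by side. When one group is completed before the other begins, the calendar carries the same information as the chart. A reader of 2.10.1 would conclude that blinding is easily secured, which the design does not support.

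Three things are at stake:

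- Knowledge of the cohort could influence outcomes that need judgement: whether a troponin rise is due to myocardial injury, stroke, and surgical site infection. It matters little for mortality or for laboratory values as such.
- Assessing the blinding is a listed objective and is meant to inform a larger study. Without a recorded measure, the review can rest only on impression.
- Infarction and injury are different events. An incidence reported under one name and collected under the other cannot be interpreted.

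**Working it through.** No figure in the plan needs re-deriving beyond 15 + 15 = 30, which agrees. The check is mainly a comparison of sections.

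**1. Does the calendar give the cohort?** Sections 2.1, 2.1.1 and 9.2 all describe a before-and-after design. The word randomisation appears in 2.5, 6.1 and 8.3, but no randomisation procedure is described. Under 2.1.1, patients 1 to 15 are controls and 16 to 30 are intervention patients. An assessor who knows the order of the cohorts but places the changeover k patients away from the true point misclassifies k patients:

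- correct = 30 − k
- k = 0: 30 of 30
- k = 3: 27 of 30 = 90%

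This shows how informative the date is. It is not evidence that any assessor knows the changeover.

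**2. Could follow-up staff know the changeover?** Section 2.6 gives identification, consent and follow-up to trained members of the research team. Section 2.9.2 has the research team apply the monitor, with readings hidden and alarms disabled in controls. Section 5.1 has site research staff record data to discharge and survival at 30 days. No section says that different individuals do these tasks, that dates or study order are withheld, or that the changeover is kept from those who follow up.

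**3. Does analyst blinding hold?** Section 2.10.1 promises it but says nothing about dates. Section 5.3 assigns a study number at treatment allocation, in an unstated format, and Section 5 and 5.3 identify participants by that number plus initials. If dates, sequential numbers or initials reach the analyst, the allocation can be worked out in the same way.

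**4. Does the review have a measure?** Sections 2.2.2 and 2.10.1 promise a review. Neither states what will be recorded.

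**5. Could recorded guesses be tested against chance?** Not safely. If the 30 guesses were independent coin tosses, 21 or more correct would have probability 0.021. With sequential cohorts, independence is the wrong model. Take an assessor who knows only that there were two consecutive blocks, picks their order by coin toss, and places the changeover uniformly at one of positions 1 to 29:

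- order right: correct = 30 − |k − 15|, where k is now the guessed position; this is 21 or more for k = 6 to 24, that is 19 of 29 positions
- order wrong: correct = |k − 15|, at most 14, so never 21
- P(21 or more) = ½ × 19/29 = 19/58 = 33%

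A threshold set for independent guesses would therefore mislead, and the guesses should only be described.

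**6. Cardiac outcome, side by side.**

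| Section | Event named | Criterion written out |
|---|---|---|
| Trial Summary | Infarction | No |
| 2.2.2 | Injury | No |
| 2.3.3 | Injury | Yes, troponin-based |
| 6.1 | Infarction | No |

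**7. How much could the counts show anyway?** Section 1.2 cites a myocardial injury rate of 2.8% in a non-cardiac surgery cohort, not in hip fracture. At that rate the expected count is 30 × 0.028 = 0.84, and the probability of no event is (1 − 0.028)^30 = 0.43. Chance dominates these outcomes at this size.

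**The case against.** The plan does not claim that blinding is certain. It allows exceptions, plans a review, and says that blinding will be altered for a larger study if required. Learning whether blinding works is a proper purpose of a feasibility study. This stands as a reason to rate the point low, but it does not repair the stated rationale or supply a measure.

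Sections 2.6 and 2.9.2 assign tasks to a team, and 2.10.1 speaks of a team performing follow-up. A reader might infer that the same people apply the monitor and assess outcomes. The documents allow that overlap but do not show it.

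The plan also uses blinded for the hidden monitor readings (2.3.2), so an assessor's guess covers only part of what the planned review could mean. That is correct, and the fix is limited to the assessor part.

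The external definitions cited in 2.3.3 may define infarction. They cannot be checked here, so it would be wrong to say that infarction is undefined. Two names for one listed outcome would still need reconciling.

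Coding of analysis files may be covered in the data management plan cited in Section 5, which is not part of these documents.

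A reader might also infer that untested patients make the incidences uninterpretable, because 3.2 takes troponin and creatinine from routine care only. The documents do not support that. The number tested can be derived from the recorded results, and completeness is already examined under 2.2.3, 2.3.1 and 5.1. What is missing is a reporting detail.

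**Conclusion.** The point holds, and its importance is minor. Not viewing the chart does not deliver follow-up blinding when cohorts run one after the other; analyst blinding is open to the same route; and the review of assessor blinding has nothing recorded to work from. The infarction and injury wording is a plain contradiction in a reported outcome.

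The rating rests on four facts: these are secondary outcomes, there are 30 patients, Section 6 plans no between-cohort test, and death and laboratory values are little affected by what the assessor knows. The blinding part assumes that follow-up staff or analysts can see surgery dates or study order and can learn the changeover. The documents leave this open.

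A reader might go further and conclude that outcomes will be biased, or that the size of the full trial will be wrong. The documents support neither: no unblinded assessment is shown, and no infarction rate is given from which to size the naming gap.

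**What to change.** 1. In 2.10, state that assessor blinding is not assured under sequential cohorts. At the end of each patient's follow-up, have the assessor record the cohort they believe the patient was in (control, intervention, do not know) and why. Tabulate the answers descriptively, with no chance-based threshold, as the measure for the assessor part of the review in 2.2.2 and 2.10.1.
2. Give the outcome analyst coded cohort labels, non-sequential identifiers without initials, and times relative to surgery. Keep calendar dates in a separate file for the recruitment rate (2.2.3), and join it to outcomes only after the blinded analysis is complete.
3. Reconcile the cardiac outcome to one event and one definition across the Trial Summary, 2.2.2, 2.3.3 and 6.1.
4. Optionally, report the number of patients with troponin and creatinine results beside each incidence.

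The cost is wording changes, one CRF question per patient and two data files in place of one, with no extra samples or visits. The downsides are a less favourable statement about blinding and the need for someone other than the outcome analyst to prepare the coded file.
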